1.0 Background

Primary monosymptomatic nocturnal enuresis (PMNE) is defined by the Diagnostic & Statistical Manual of Mental Disorders (DSM- IV) as an involuntary voiding of urine during sleep, with a severity of at least twice a week, in children aged >5 years in the absence of congenital or acquired defects of the central nervous system(1-3). Other etiologies that cause bed wetting such as cardiopulmonary, neurologic, endocrine or urologic diseases should be ruled out (1). Secondary nocturnal enuresis is defined nocturnal enuresis after at least 6 month of continuous dryness without prior without intervention (1, 4).

PMNE affects 10-20% kids at 5 years old (1, 4, 5). It does resolve spontaneously so that 5% of 10 year olds and 1% of 15 year olds are still affected (2-4). Is more common in boys. While the disease its self is benign, and improves without intervention, it does pose a significant social and emotional burden on the child and their family. These include parental disapproval, sibling teasing, and inability to attend sleep overs with peers, all of which lead to families seeking treatment options (3, 4).

Current treatments start with conservative management. This includes appropriate fluid intake, scheduled toileting during the day, avoidance of bladder irritants and constipation (4, 5). If these fail to improve symptoms or families are looking for a more active form of treatment, first line therapy is either a bed wetting alarms or desmopressin (1, 4, 5).

Bed wetting alarms typically attach to the child's clothes and sound when the device gets wet with urine. The goal of these devices is to alert the child that he or she has started to urinate and to allow them to be woken up, then voluntarily complete the void in the bathroom (1, 3, 6). While these devices are effective, they take about 4 weeks of constant use to show significant improvement and require continued use for at least 3 months to gain durable results (2, 5, 6). Alarms also suffer from a high discontinuation rate, as high as 30% (2, 3, 6). Problems associate with disruption of other family members, difficulty using the devices, and the device failing to cure PMNE have all been cited by families and reasons they stopped using the device (3, 6).

Desmopressin works as a vasopressin analogue to decrease urine production at night (1, 2, 4). It is quicker to improve symptoms compared to alarms once the treatment is discontinued the recurrence of PMNE is significantly higher than alarm devices (2, 4, 6).

The Lully Sleep Guardian was initially developed for use in night terrors. The device works by programing a vibrating disk that is placed under the child's bed to alter sleep patterns and prevent the onset of sleep terrors. The child is not woken up for the treatment of sleep terrors. The device has also be shown to anecdotally improve users' nocturnal enuresis. There have been no reports of safety concerns or hazards with the device (7, 8).

2.0 Rationale and Specific Aims

Aim 1: Determine the effectiveness of scheduled awakenings, with the Lully Sleep Guardian, in patients with PMNE, at reducing the frequency of bed-wetting.

3.0 Inclusion/Exclusion Criteria

Inclusion Criteria	Exclusion Criteria

 • Benign nocturnal enuresis • Age: 5 – 17 • Access to an Apple iPhone, iPad, or iPod Touch preferred. (Will have a limited number if ipods available for loan if needed) 	
 • Diurnal Enuresis • Constipation • Neurogenic Bladder • Any serious underlying cardiopulmonary problems that require diuretics or antihypertensive medications to manage • Any bladder active medications • Age: < 5 years of age; > 17 years of age • Cerebral Palsy • Mental disorders, mood disorders, or autism-spectrum disorder • Epilepsy or seizure history • Restless leg syndrome • Use of benzodiazepine/clonidine

4.0 Enrollment

Patient Identification, Recruitment, Eligibility Determination

Participants may be recruited from the pediatric urology clinic at Riley Hospital for Children. These patients may be established patients, new patients, or referrals to Pediatric Urology not yet seen in clinic. We will also accept potential participants who are not affiliated with the Pediatric Urology clinic but meet inclusion criteria and have interest. These possible participants include those who attend bedwetting seminars conducted by Pediatric Urology and those who respond to advertising in the community. Potential participants may be recruited from the community through the use of flyers, social media, and INResearch

The initial contact with potential participants may be in person, by phone, or by email. A research team member will provide an overview of the study and be available to answer any questions posed by the family and/or patient. If the family has ongoing interest, they will be asked to complete screening questions to determine if the child meets the eligibility criteria for this study. If a potential participant responds directly to the flyer, they have the option to answer eligibility questions before interaction with a study team member.

To confirm potential participant does not meet any of the exclusion criteria and is eligible, the parent and participant will be asked to together complete two screening questionnaires, the Lully Q &A and the Vancouver questionnaire . Questionnaire results will be reviewed by a study team member and eligibility will be determined.

Consent Procedures

If the candidate is eligible, the informed consent, the assent (if applicable) and the HIPAA authorization will be obtained to enroll the patient. Informed consent and authorization procedures may occur in person or via phone. In either circumstance, the research team member will obtain written signature of consent and authorization. For children 7 – 17 years old, we will obtain child assent in addition to parents informed consent. After consenting, the participant will be immediately assigned to a treatment arm.

Treatment Arms

This study will enroll a total of 40 patients, with 20 in each treatment arm.

The first 20 subjects enrolled are scheduled to complete the study phases (S1 and S2) in the following order: 6 weeks of behavioral modifications plus the Lully device, followed by 6 weeks of behavioral modifications only (without the device). Subsequently, the last 20 subjects enrolled will undergo the study phases in the reverse order: 6 weeks of behavioral modifications only, followed by 6 weeks of behavioral modifications plus use of the Lully device. This crossover will increase the validity of findings, but also ensure ease and simplicity when following patients.

The Lully device will be labelled in accordance with FDA investigational labelling requirements.

.

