5.0 Study Procedures

During the initial and therapeutic phases of this study, participants are asked to enter responses daily into a Lully Study app. When the parent sets up the app, they enter their study email address, which is in the format [contact]. The app will send a prompt each morning. The questions the participant is prompted to answer are: Did your child have a bed wetting episode last night? What time was it?

In a free text box the family is asked to add additional information to describe how wet the child was using the following 1-5 scale: 1- wet underwear; 2-wet underwear and damp pajamas; 3-soaked underwear, pajamas; 4-soaked pajamas, damp mattress; 5- soaked mattress

Initial Phase to establish baseline(4 wks)

1. The family will complete a QOL survey, the KIDSCREEN 27 before starting the initial 4 week phase.
2. The family will receive further counseling on behavioral modifications. Handout available for reference in Notes and Attachments.

3. Family will be provided with Malem Enuresis alarm to be used daily during 2 weeks of baseline data collection
4. Family will be asked to complete the KIDSCREEN 27 and the Vancouver questionnaire before starting therapeutic phase

Therapeutic phase

1. Each participant will complete the study phases (S1 and S2) in the order determined by their assigned treatment arm
2. During the 6 weeks of scheduled awakening protocol using Lully Sleep Guardian: each night, a scheduled awakening will be performed with the Lully pod. This will be used to reliably produce a brief awakening by titrating the device to a minimal awakening stimulus during the first night of use. If the brief awakening cannot be produced using the Lully pod, the parent will gently awaken the child
3. The family will complete the KIDSCREEN 27 and the Vancouver questionnaire at the cross-over between the study phases (S1 and S2) and at the completion of their 2 study phase

Study Completion

Family will be asked to return any equipment loaned for the purposes of this study to the Pediatric Urology Clinic at Riley

Compensation

Patient and families will be compensated with \$1 per day for each day they respond to the daily questions prompted by the app about their child's nocturnal enuresis are replied to and an additional \$5 per round of QOL surveys (2 surveys per round). The total will be summed at the conclusion of the study and paid to the participant as an Amazon gift card.

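### The order of phases is assigned at consent, four weeks before it takes effect, so children lost during baseline have already used a place and that loss can depend on arm

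*Protocol*

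**What the plan says.** Section 4.0 (Consent Procedures) makes consent the point of enrolment: "the informed consent, the assent (if applicable) and the HIPAA authorization will be obtained to enroll the patient". It then continues: "After consenting, the participant will be immediately assigned to a treatment arm".

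Section 4.0 (Treatment Arms) gives the size: "This study will enroll a total of 40 patients, with 20 in each treatment arm". Places are filled by order of enrolment. One sequence is defined by "The first 20 subjects enrolled are scheduled to complete the study phases (S1 and S2) in the following order", with the device phase first. For the other, "the last 20 subjects enrolled will undergo the study phases in the reverse order".

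Section 5.0 places a run-in between assignment and the first study phase (S1): "Initial Phase to establish baseline(4 wks". It includes behavioral counseling, daily app entries on bed-wetting and an alarm: "Family will be provided with Malem Enuresis alarm to be used daily during 2 weeks of baseline data collection". The assigned order governs only S1 and S2, which follow. Section 7.0 allows withdrawal at the family's request or by the principal investigator. The protocol describes neither replacement of children lost during baseline nor concealment of the order.

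**The concern.** The order matters only from S1, yet it is fixed four weeks earlier, ahead of the run-in. Three things follow.

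- **Places are used up.** A child who stops during baseline already counts among the 20 but contributes nothing to the comparison of device and no-device phases.
- **Loss can depend on arm.** Once the order is assigned, leaving before S1 is a post-assignment event. If one order is less attractive to families who know it, the children who remain in the two sequences may differ.
- **Baseline reporting is not protected.** Wetting is reported by the family. Nothing in sections 4.0 or 5.0 keeps the family from knowing its order while it reports baseline.

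Section 8.0 intends to use this study for the power calculation of a later trial. Lost crossover data, and losses that cannot be separated from the arm, would weaken that use. The fault is one of timing: it would remain if the order were drawn at random at consent.

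**Working it through.** **Inputs from the protocol.** 40 enrolled, 20 per sequence (section 4.0); assignment at consent (4.0); baseline of 4 weeks before S1 (5.0). The plan's own figure reproduces as a sum, 20 + 20 = 40. No significance level, power, effect size or standard deviation is given, so 40 cannot be checked against a power formula.

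**Assumption.** The protocol gives no baseline drop-out rate. I use d = 10%, 20% and 30%, equal in both arms unless stated otherwise, with no replacement.

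**Step 1: numbers entering S1.** Expected total = 40(1 − d). With equal losses the standard error rises by √(1/(1 − d)). The numbers remaining are two independent Binomial(20, 1 − d) counts, n1 and n2.

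| d | Expected to start S1 | SE factor | P(both keep 20) = (1 − d)^40 | P(n1 and n2 differ by ≥ 4) |
|---|---|---|---|---|
| 10% | 36 | 1.05 | 1.5% | 6% |
| 20% | 32 | 1.12 | 0.01% | 16% |
| 30% | 28 | 1.20 | < 0.01% | 23% |

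**Step 2: precision lost through imbalance alone.** The variance of the period-adjusted estimate is proportional to 1/n1 + 1/n2. Efficiency relative to equal sequences of the same total N is (4/N)/(1/n1 + 1/n2).
- 20 and 16: (4/36)/(1/20 + 1/16) = 0.1111/0.1125 = 98.8%.
- 18 and 14: (4/32)/(1/18 + 1/14) = 0.1250/0.1270 = 98.4%.

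Imbalance costs little. The loss of children is the larger cost.

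**Step 3: period bias if period is ignored.** Let π be the change from S1 to S2 unrelated to the device. The device-minus-control difference carries −π in device-first children and +π in device-second children. The simple mean of all differences therefore carries a share |n1 − n2|/(n1 + n2) of π. For an illustrative arm-dependent loss of 2 of 20 against 6 of 20, this is (18 − 14)/32 = 12.5%. With period in the model it is zero.

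**Step 4: later assignment under the present allocation rule.** Suppose 40 are consented, 20% leave during baseline, and the first-20/last-20 rule is then applied to children entering S1. The first sequence fills to 20 and the second receives 32 − 20 = 12. All the loss falls on the second sequence, and the share in step 3 becomes (20 − 12)/32 = 25%. Moving the date without changing how the order is balanced makes this worse.

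**Step 5: consents needed for 40 starters.** 40/(1 − d), rounded up: 45, 50 and 58 at 10%, 20% and 30%.

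**The case against.** The strongest reply is that little of this harms the comparison the trial makes.

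- **Disclosure.** A reader might infer that families report baseline knowing what comes next. The protocol says only that the participant is assigned. Disclosure at consent is plausible, since nothing conceals the order, but it is not stated. Also, the design compares device and no-device phases within each child, and families know which phase they are in anyway. Nor is every pre-treatment measure exposed, because the Vancouver questionnaire is also completed at screening, before consent. This stands: the baseline issue is a missing safeguard and not a demonstrated bias.
- **Balance.** A reader might infer that a crossover needs equal sequences. It does not, as step 2 shows. The 12.5% presumes an analysis that omits period, and the analysis model may be set in an SAP that is not shown. This stands.
- **Size of the trend.** Section 1.0 says of the condition: "It does resolve spontaneously so that 5% of 10 year olds and 1% of 15 year olds are still affected". If that decline is taken as exponential, it is ln(5)/5 = 0.32 per year, or about 3.7% over 6 weeks, and 12.5% of that is about 0.5%. This stands for natural resolution. Trends from counseling or the alarm weeks could be larger, but the documents give no size for them.
- **The number 40.** It is an enrolment figure. No number of completed pairs is promised and no power target is breached. This stands.
- **Attrition.** The figure of up to 30% in section 1.0 is alarm discontinuation, in a paragraph about use over months. It is not study drop-out after 2 weeks of alarm use. The split of 2 against 6 is illustrative. Both sequences receive the device, and daily responses are paid. This stands: all the loss rates are assumptions.
- **The remedy.** Under first-20/last-20, staff can predict the order whenever it is formally assigned. This stands, and the fix must allow for it.

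None of this answers the core point. Modeling period does not restore lost children or undo arm-related selection, and no analysis plan can move the moment of assignment.

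**Conclusion.** The point holds in a limited form. Section 4.0 fixes the order at consent and counts places there, while section 5.0 delays any use of the order by four weeks. The main effect is fewer children contributing S1 and S2 data: 36, 32 or 28 of 40 under assumed losses of 10%, 20% or 30%. With this comes the possibility of arm-related selection between assignment and S1. Exposure of baseline reports to knowledge of the order is possible but not documented. Bias from a time trend arises only if the analysis ignores period, and unequal numbers alone cost about 1% to 2% of efficiency in the examples of 20/16 and 18/14.

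The figures rest on assumed loss rates and on no replacement of children who leave. The change is worth making because it is nearly free. It is secondary to the allocation by order of enrolment, a separate and larger flaw whose predictability later assignment does not remove.

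**What to change.** Replace the assignment sentence in section 4.0 with wording such as: *The order of the study phases is assigned, and disclosed to the family, on the day the baseline phase is completed, immediately before S1.* Allocate 1:1 among children who enter S1, and report those who leave during baseline separately as unassigned.

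Then choose one of two ways to count:
- **Fill 20 per sequence at S1 entry.** This needs about 45, 50 or 58 consents at an assumed 10%, 20% or 30% loss.
- **Keep 40 consents.** State that fewer than 40 will enter S1, and balance the order among those who do, for example in concealed blocks. The first-20/last-20 rule cannot be kept here, because it would place every baseline loss in the second sequence.

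A concealed allocation is needed in either case if the order is not to be predictable.

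Cost: a short amendment to section 4.0, with no added study procedure for families. Device logistics would be settled at week 4 and not at consent, and the first option needs some extra consents. Losses during S1 and S2 can still unbalance the sequences, and this change does not address them.

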8.0 Statistical Considerations

This study is a simple effectiveness trial to determine if the Lully Sleep Guardian has any effect on benign nocturnal enuresis. If an effect is shown, the research team will use this study to perform a power calculation and facilitate a comparative effectiveness trial comparing Lully Sleep Guardian to current standards of care.

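### Crossover order is fixed by enrolment rank (first 20 device-first, last 20 control-first), so it is foreseeable and confounded with enrolment period

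*Protocol*

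**What the plan says.** Section 4.0 (Treatment Arms) sets the size: "This study will enroll a total of 40 patients, with 20 in each treatment arm". It then sets the order: "The first 20 subjects enrolled are scheduled to complete the study phases (S1 and S2) in the following order", namely six weeks with the device plus behavioral modification, then six weeks of behavioral modification only; "the last 20 subjects enrolled will undergo the study phases in the reverse order". The design is justified partly by simplicity of follow-up and partly by this claim: "This crossover will increase the validity of findings".

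The same section describes entry to the study. "Questionnaire results will be reviewed by a study team member and eligibility will be determined", and "After consenting, the participant will be immediately assigned to a treatment arm".

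Section 5.0 places a four-week baseline before the two six-week phases. Section 8.0 states the use of the result: if an effect is shown, "the research team will use this study to perform a power calculation" for a later comparative trial.

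The protocol nowhere mentions randomization, alternation or concealment, and it does not claim to be randomized.

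**The concern.** Reversing the order in half the children is meant to separate the device effect from whatever changes between the first phase (S1) and the second (S2) anyway. That works only if the change unrelated to the device is, on average, the same in both order groups. Randomization secures this in expectation; filling one order completely before opening the other does not. Here the device-first children are the early cohort and the control-first children the late one. Season, school term or a shift among the recruitment routes listed in section 4.0 (clinic, referrals, seminars, flyers, social media) could make the S1-to-S2 change differ between them.

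Three further consequences follow.

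- Whoever judges eligibility can know the next child's order. This comes from the deterministic rule itself, not from assignment soon after consent.
- Any comparison of the two orders, including a check for carryover, is also a comparison of early with late enrollees. Analysis cannot separate the two without further assumptions.
- The orders fill one after the other, so a shortfall is lost wholly from control-first.

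A biased estimate would then pass into the planning of the next trial.

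**Working it through.** **Inputs from the protocol.** 40 children, 20 per order; ranks 1–20 device-first, ranks 21–40 control-first (section 4.0); four-week baseline, then two six-week phases, so 4 + 6 + 6 = 16 weeks per child (sections 4.0 and 5.0). The stated split is consistent: 20 + 20 = 40. No wet-night rate, standard deviation or seasonal effect is given.

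**Separation in time.** Mean enrolment rank is (1 + 20)/2 = 10.5 for device-first and (21 + 40)/2 = 30.5 for control-first, a difference of 20. If a 20:20 split were shuffled at random, the difference would have mean 0 and standard deviation about 3.7. Under the stated rule 40 of 40 assignments can be predicted. Under a full random shuffle, a best guesser who knows all past assignments gets about 23.5 of 40; short blocks are somewhat more predictable than that.

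**Bias formula.** Let τ be the device effect, and let π_D and π_C be the mean S2-minus-S1 changes unrelated to the device in the device-first and control-first groups. The crossover estimate is

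est = ½[mean(S1 − S2) in device-first + mean(S2 − S1) in control-first],

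so E[est] = τ + (π_C − π_D)/2.

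With assumed changes in wet nights per week:

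| π_D | π_C | Bias |
|---|---|---|
| −1 | −1 | 0 |
| −1 | −0.5 | 0.25 |
| −1 | 0 | 0.5 |
| −0.5 | +0.5 | 0.5 |

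**Illustration with a seasonal wave (assumed).** Take A·sin(ωw + φ), with ω = 2π/52 per week, and even enrolment over W weeks. A child enrolled at week t has S1 from t+4 to t+10 and S2 from t+10 to t+16. Averaging over each phase and subtracting gives

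π(t) = 2A·[sin(3ω)/(3ω)]·sin(3ω)·cos(ω(t+10) + φ).

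With sin(3ω) = 0.355 and sin(3ω)/(3ω) = 0.978, the multiplier is 2 × 0.978 × 0.355 = 0.694.

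Averaging over each half of enrolment and halving the difference gives, with x = ωW/4:

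worst-phase |bias|/A = 0.694·sin²(x)/x, and the mean over phases is 2/π times that.

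| W (weeks) | x | Worst phase | Mean over phases | Best phase |
|---|---|---|---|---|
| 13 | 0.393 | 0.26 | 0.16 | 0 |
| 26 | 0.785 | 0.44 | 0.28 | 0 |
| 36 (= 52 − 16) | 1.087 | 0.50 | 0.32 | 0 |

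For assumed amplitudes of 0.25, 0.5 and 1.0 nights per week, the worst-phase bias is 0.06–0.13, 0.13–0.25 and 0.26–0.50 nights per week.

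**Same wave under randomization.** With four blocks of 4 and four of 6 in random order, at the same worst phase, the expected bias is 0. For W = 13, 26 and 36, 95% of lists stay within 0.013, 0.020 and 0.024 of the amplitude. If block sizes are drawn at random and the list is cut at 40, the limits are about 0.03 to 0.04.

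**Shortfall.** If accrual stopped at 30, the split would be 20:10. The period-adjusted variance would be (1/20 + 1/10)/(1/15 + 1/15) = 1.125 times that of 15:15. If it stopped at 20, only one order would exist.

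**The case against.** The best defense is that the rule is stated openly, is never called randomized, and suits a small, simple study that precedes a comparative trial. Counterbalancing does improve on a single-order before-and-after design. Every child receives the device, so staff have little reason to steer enrolment, and it is hard to see how they would select on a child's future change. All of this stands. It makes the point a weak design choice rather than a contradiction, and makes foreseeability secondary. It does not touch the confounding of order with enrolment period, which needs no steering.

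The size is also unknown. The amplitudes are assumed, the bias may be zero, and 36 weeks of enrolment leaves no separate time in the one-year plan of section 10.0 for start-up and analysis. If enrolment overran, the worst-phase figure would fall: 0.44 at 52 weeks, 0.15 at 78 and zero at 104. These limits are accepted.

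Finally, because entries are daily and the cohorts' calendar windows can overlap, an analysis with calendar-week effects could remove a season common to all children. The device effect then stays estimable, but with only about 29–42% of the information (independent errors assumed). That means a variance about 2.4 to 3.4 times as large (1/0.42 to 1/0.29). Changes specific to one cohort, such as those from a different recruitment source, would remain.

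**Conclusion.** The concern holds. Order is set by enrolment rank, known in advance and inseparable from enrolment period, so the crossover does not have the protection that randomizing the order would give. The device effect is biased by half of any difference between the two cohorts in their S1-to-S2 change.

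How large that is cannot be known from the protocol. Under an assumed 52-week wave with even enrolment over 13 to 36 weeks, it ranges from zero to 0.26–0.50 of the amplitude, depending on timing. Stable differences between children and any common period change do cancel. The point merits correction before enrolment rather than alarm: the change is cheap, and once enrolment is over the confounding can be repaired only in part and at a considerable loss of precision.

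**What to change.** Replace the first-20/last-20 rule in section 4.0 with concealed 1:1 randomization to order, in permuted blocks of varying size. Four blocks of 4 and four of 6 in random order give 4 × 4 + 4 × 6 = 40 children, 20 per order. The list should be kept from those who judge eligibility and obtain consent.

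Preferably, reveal the order at the end of baseline, just before S1, and amend the sentence on immediate assignment to match. Section 5.0 already has a step there: "Family will be asked to complete the KIDSCREEN 27 and the Vancouver questionnaire before starting therapeutic phase". It does not say how families are contacted at that step, so whether any extra contact is needed should be confirmed. Concealment matters more than this timing; a concealed list opened after consent would also prevent foreseeability.

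If children are already enrolled, randomize the rest and report the earlier ones as non-randomized. With 10 or 20 already device-first, the expected split is 25:15 or 30:10. The period-adjusted variance is then (1/25 + 1/15)/(1/20 + 1/20) = 1.07 or (1/30 + 1/10)/(1/20 + 1/20) = 1.33 times that of 20:20.

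If the rule is kept, describe the study as a non-randomized crossover and qualify the validity claim in section 4.0.

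The cost is two protocol sentences and a generated list, with no extra children. Staff would run both orders at once and lose some of the simplicity the protocol values. The effect on device supply cannot be judged, because no inventory is given.

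### With no washout stated between the two 6-week phases, should the first 2 weeks of each phase be left out of the main comparison?

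*Protocol*

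**What the plan says.** Section 4.0 (Treatment Arms) assigns the first 20 children enrolled to "6 weeks of behavioral modifications plus the Lully device, followed by 6 weeks of behavioral modifications only (without the device"), and the last 20 to the same phases in reverse. It adds: "This crossover will increase the validity of findings". Section 5.0 (Therapeutic phase, item 3) places questionnaires "at the cross-over between the study phases (S1 and S2) and at the completion of their 2 study phase". It describes no interval, discarded nights or carryover provision at that point. Bed-wetting is recorded nightly: "The app will send a prompt each morning".

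Section 8.0 gives the purpose as "to determine if the Lully Sleep Guardian has any effect on benign nocturnal enuresis". It names no estimator, analysis window, effect size or standard deviation.

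On what happens after treatment stops, the protocol speaks only of other treatments. Section 1.0 says of desmopressin that "once the treatment is discontinued the recurrence of PMNE is significantly higher than alarm devices". Of alarms it says that "they take about 4 weeks of constant use to show significant improvement" and that they "require continued use for at least 3 months to gain durable results". It says nothing about persistence with the vibrating device.

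**The concern.** A two-period crossover compares each child with himself or herself, which is clean only if the device effect ends when the device is removed. Children who start on control cannot carry a device benefit into their control phase; children who start on the device can. Reversing the order for half the children removes a time trend common to both sequences, but it does not remove this one-sided leak. The statement in Section 4.0 that the crossover improves validity therefore rests on an unstated assumption of no carryover.

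At stake is a bias toward no effect in a study that asks whether there is any effect, and whose result is meant to feed the power calculation for a later trial. Because the app already collects nightly data, leaving out the first 2 weeks of each phase looks like a nearly free remedy.

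**Working it through.** The protocol states no power, effect size or standard deviation, so there is no figure of its own to reproduce.

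**Inputs from the protocol.** 40 children, 20 per sequence (Section 4.0); 6 weeks per phase, so 6 × 7 = 42 nights, or 4 × 7 = 28 after dropping 2 weeks; nightly recording (Section 5.0).

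**Assumptions, none of them in the protocol.** Carryover decays exponentially with half-life h of 1, 2 or 4 weeks. The device effect is τ = 0.5 or 1 night/week and is constant within a phase. The wet-night probability is 0.5, nights are independent, and every night is logged. The between-child SD of the true difference is 0 to 2 nights/week.

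**Bias.** Let π be the period trend and c the mean share of the effect that persists over the control nights analysed.
- Device-first difference: τ − (π + cτ)
- Control-first difference: τ + π
- Average: τ(1 − c/2)

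The trend cancels and the carryover does not. With the window running from week a to week b after stopping, c = h/(ln 2 · (b − a)) · (2^(−a/h) − 2^(−b/h)).

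| h (weeks) | c, all 6 weeks | retained | c, weeks 3–6 | retained | ratio of retained |
|---|---|---|---|---|---|
| 1 | 0.237 | 0.882 | 0.085 | 0.958 | 1.09 |
| 2 | 0.421 | 0.790 | 0.271 | 0.865 | 1.10 |
| 4 | 0.622 | 0.689 | 0.510 | 0.745 | 1.08 |
| no decay | 1 | 0.500 | 1 | 0.500 | 1.00 |

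A rebound after stopping would bias the other way: c = −0.25 gives 1 + 0.125 = 1.125.

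**Precision.** SE = √[(49 · 2 · 0.25/n + SD²)/40] nights/week.
- SD 0: 0.121 with n = 42, 0.148 with n = 28 (+22%)
- SD 1.5: 0.266 and 0.280 (+5%)

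**Bias and precision together.** RMSE = √[(τc/2)² + SE²], at SD 0, all 6 weeks → weeks 3–6:

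| h (weeks) | τ = 1 | τ = 0.5 |
|---|---|---|
| 1 | 0.169 → 0.154 | 0.134 → 0.149 |
| 2 | 0.243 → 0.200 | 0.160 → 0.163 |
| 4 | 0.334 → 0.295 | 0.197 → 0.195 |

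The shorter window wins only when τ exceeds √[(SE₂₈² − SE₄₂²)/((c₄₂/2)² − (c₂₈/2)²)], which is 0.77, 0.53 and 0.48 nights/week for h = 1, 2 and 4; SD cancels from this expression. The threshold moves with the other assumptions:
- 60% of nights logged: 1.00, 0.68, 0.62
- Night-to-night autocorrelation 0.3, first-order: 1.03, 0.71, 0.64
- Wet-night probability 0.3: 0.71, 0.49, 0.44

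**Detection.** Estimate/SE at τ = 1, all 6 weeks → weeks 3–6:

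| SD | h = 1 | h = 2 | h = 4 |
|---|---|---|---|
| 0 | 7.30 → 6.48 | 6.54 → 5.85 | 5.71 → 5.04 |
| 1 | 4.43 → 4.42 | 3.97 → 3.99 | 3.46 → 3.44 |
| 1.5 | 3.31 → 3.43 | 2.97 → 3.09 | 2.59 → 2.67 |
| 2 | 2.60 → 2.74 | 2.33 → 2.48 | 2.04 → 2.13 |

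This is worse at SD 0, flat at SD 1, about 3–4% better at SD 1.5 and about 5–6% better at SD 2.

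**Target.** If the effect varies over the phase, the window changes what is estimated. An effect building linearly over 4 weeks averages 0.667 of its final value over weeks 1–6 and 0.875 over weeks 3–6 (ratio 1.31). One fading linearly to half over 6 weeks averages 0.750 and 0.667 (ratio 0.89). In the fading case, take carryover as starting from the end-of-phase effect of 0.5. The expected estimate is then 0.69, 0.64 and 0.59 with all nights, against 0.65, 0.60 and 0.54 with weeks 3–6. The shorter window lies further from the 6-week mean of 0.75 at every half-life.

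**The case for a change.** The strongest case for a change is that the consecutive phases and the claim of improved validity are protocol text, not details awaiting an analysis plan. Section 1.0 itself treats durability after stopping as a feature that differs between enuresis treatments. The bias is systematic and grows with the effect, whereas the loss of precision is modest if children differ in response. An underestimated effect would also carry into the planned power calculation: at a 2-week half-life, required sample size scales as 1/0.790² = 1.60 with all nights and 1/0.865² = 1.34 with weeks 3–6. The remedy would cost a few sentences.

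Part of this stands. The validity statement does depend on an absence of carryover that the protocol does not discuss, and for any carryover that declines over time the later window is less biased.

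The step to a required change does not stand. The alarm and desmopressin remarks are analogies, and the one durability figure for alarms concerns at least 3 months of use against 6 weeks here. With no true effect the modelled bias τc/2 is zero, so it cannot create a false positive; an attenuated estimate makes a later sample size larger, not too small. A comparison of first phases alone would avoid carryover, but sequence follows enrolment order, so it has its own confounding. The end-of-phase questionnaires gain nothing from a diary window.

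**Conclusion.** No change to the plan follows. The mechanism is correctly identified: with no interval stated, persisting benefit enters one cell of the design and shrinks a simple pooled contrast by c/2, or 12% to 31% for assumed half-lives of 1 to 4 weeks and 50% under full persistence. A 2-week analytic washout cuts the first range to 4% to 25% and leaves the second untouched.

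Against that, it discards a third of the nights and raises the SE by 3% to 22% for between-child SDs of 2 down to 0. It yields essentially no RMSE gain near 0.5 nights/week, and it can move the estimand (1.31 or 0.89 in the examples) by more than the 1.08–1.10 rise in retained effect. This is a trade-off whose sign depends on persistence, effect size, between-child variation and diary completeness, none of which the protocol gives.

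The protocol fixes no estimator or window, so no stated rule is wrong. Choosing the diary nights is work commonly left to a statistical analysis plan, and the nightly data allow either choice. An analyst can sensibly report weeks 3–6 beside all 6 weeks as a sensitivity analysis, and a reader should take the validity statement in Section 4.0 as conditional on little carryover. All magnitudes rest on the assumed half-lives, effects, SDs, wet-night probability and night independence shown above.
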